### **13.7.3 Vital signs**

All vital sign measurements will also be presented in a by-subject listing.

### **13.7.4 Physical examinations**

All abnormal physical examination data will be presented in a by-subject listing.

### **13.7.5 Electrocardiograms (ECG)**

Observed values and change from baseline for continuous ECG parameters (ECG Heart Rate (beats/min), QRS Duration (ms), PR Interval (ms), RR Interval (ms), QT Interval (ms), QTc Interval

(ms)) will be listed by cohort, and scheduled visit. The listing will include overall ECG interpretation categorized as “Normal”, “Abnormal, not clinically significant”, and “Abnormal, clinically significant”. Since post-baseline values are collected only at the discretion of the Investigator, no summary table is planned.

**13.7.6 Eastern Cooperative Oncology Group (ECOG) performance status**

Shift tables of ECOG performance status from baseline to worst post-baseline values, and to each post-baseline visit will be summarized by cohort/dose level and scheduled visits.

A by-subject listing of ECOG results will also be provided.

**13.8 Other Analysis**

**13.8.1 Pharmacokinetics analysis**

Not applicable.

**13.8.2 Pharmacodynamics/immunogenic response analysis**

The pharmacodynamic response to ELI-002 2P will be assessed by evaluation of immunogenic responses to the vaccine. PD (Pharmacodynamic) /Biomarker Evaluable Set will be used for tumor biomarker and PD endpoints. Safety analysis set will be used for other summary tables.

A subject level listing will be provided for all immunogenic responses listed in Table . Summary tables will be provided for the Safety Analysis Set, unless otherwise specified.. In addition a waterfall plot of subject’s best tumor responses on percent change from baseline among ctDNA, and all serum biomarkers CA19-9and CEA will be presented.

Additional analyses of Immunogenicity are beyond the scope of this Statistical Analysis Plan and is specified in a separate addendum attached as an appendix in this document.

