### **13.3.3.2. Analysis of Biomarker Response**

Response will be defined as any subject with a reduction or clearance of biomarker (ctDNA or serum tumor biomarker) compared with baseline [[Tie et al, 2019](#)]. Subjects who do not attain a response for any reason (eg, missing data due to withdrawal) will be counted as non-responders. The subset of subjects with biomarker clearance will also be summarized.

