#### 9.1.2 Phase 1 Secondary Endpoint

- To report the proportion of subjects with ctDNA reduction and clearance, defined as reduction or clearance in ctDNA compared to baseline, or if ctDNA was not detectable at baseline, serum tumor biomarker (such as CA19-9, CEA, and CA-125) reduction and clearance compared to baseline

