### 11.0 ANALYSIS POPULATIONS

#### 11.1 Full Analysis Set

The Full Analysis Set (FAS) will include all subjects who received any amount of ELI-002-2P vaccine. This population will be used for summaries of subject demographics, and baseline characteristics. Additional exploratory analyses may be performed for the subjects treated at the MTD and doses lower than the MTD at which biomarker (ctDNA, or if ctDNA was not detected at baseline, serum tumor biomarker) clearance/reduction is observed.

Planned treatment received will be used for FAS.

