#### 11.4 PD (Pharmacodynamic)/Biomarker Evaluable Set (PDS)

The PD/Biomarker Evaluable Set will include subjects who receive any amount of trial treatment, with the additional requirement that relevant blood sampling data at the appropriate assessment time point(s) must be available for inclusion in the analysis for any PD parameter.

The PDS analysis set will be used for summary of Pharmacodynamic endpoints and biomarkers.

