## 12.2 Handling of Missing Data

In the case of progression free survival or overall survival analyses, missing data will be handled through the use of censoring at the “date of last tumor assessment”, or “date last known to be alive,” respectively (Details see Table ). In the case of missing data for all other analyses, there will be no data imputation (i.e., missing data will be left as missing), unless otherwise specified.

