**13.6.1 Analysis methods and censoring**

The statistical analysis methods for RFS, 1-Year RFS and OS are summarized in Table 15. Unless otherwise stated, the full analysis set (FAS) will be the primary analysis set for all efficacy endpoints.

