### **1.5. Population Definitions**

The following patient populations will be evaluated and used for presentation and analysis of the immunogenicity or ctDNA biomarker data:

- Immunogenicity Population: All patients who receive any amount of study treatment and contribute any immunogenicity data.
- ctDNA Population: All patients who receive any amount of study treatment and contribute any ctDNA data.

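### The SAP does not carry over the protocol's rule that missing counts as non-response for the biomarker response rate, so the rate it reports can only err upward against that rule

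*SAP*

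**What the plan says.** The secondary endpoint in SAP 9.1.2 is "To report the proportion of subjects with ctDNA reduction and clearance", with a serum marker standing in when ctDNA was not detectable at baseline. Protocol 6.2.2 has the same endpoint.

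Protocol 13.3.3.2 sets the missing-data rule for it: "Subjects who do not attain a response for any reason (eg, missing data due to withdrawal) will be counted as non-responders". The protocol's Disease Response Evaluable Set (13.2.2.3) is for supportive analysis only. It also keeps a subject who has had a recurrence or died without any post-baseline sample.

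The SAP handles the endpoint differently in four places.

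- SAP 13.8.2: "PD (Pharmacodynamic) /Biomarker Evaluable Set will be used for tumor biomarker and PD endpoints".
- SAP 11.4, defining that set (the PDS): "relevant blood sampling data at the appropriate assessment time point(s) must be available for inclusion in the analysis for any PD parameter".
- SAP 12.2, outside the survival endpoints: "there will be no data imputation (i.e., missing data will be left as missing), unless otherwise specified".
- SAP Table 8 defines reduction and clearance without a non-responder rule, and disregards results obtained after new anti-cancer therapy has begun.

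The addendum attached to the SAP has its own set in section 1.5: "ctDNA Population: All patients who receive any amount of study treatment and contribute any ctDNA data". Its section 2.2 and Table 7 report a response rate but give neither a denominator nor a rule for missing values.

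SAP 14.0 reports that the Disease Response Evaluable Set was dropped. It does not mention the choice of the PDS for this endpoint or the absence of the non-responder rule. The revision history mentions updated biomarker definitions and analyses only in general terms.

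**The concern.** A subject who dies, withdraws, or relapses clinically and starts other therapy before the first usable sample is a failure under the protocol. If the rate is taken on subjects with samples, that subject leaves the denominator instead. The protocol's two protections for such subjects, the non-responder rule and the supportive set that kept early events, are both absent from the SAP.

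The rate will be read outside this trial. Protocol 4.6.5 presents a residual-disease response as preliminary proof of concept, and SAP 13.1 says the efficacy summaries are meant to inform the design of later studies. With 3 to 6 subjects per cohort, one subject more or less in the denominator visibly changes a cohort's rate.

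A smaller, related point concerns the optional exploratory analysis in Protocol 13.2.2.1 and SAP 11.1. It may combine the MTD with "doses lower than the MTD at which biomarker (ctDNA, or if ctDNA was not detected at baseline, serum tumor biomarker) clearance/reduction is observed". That chooses the lower dose levels by the outcome being summarised.

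**Working it through.** **Inputs.** Planned enrolment is about 18, in three cohorts of 3 to 6 (Protocol 13.1): 3 × 3 = 9 at the least and 3 × 6 = 18 at the most, so the stated figure is the upper end. SAP 8.1 lists two further cohorts, so up to 5 × 6 = 30. The documents give no expected response rate and no number without a post-baseline sample; both are assumed below and varied.

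**Formula.** Let N be the number treated, r the responders, and m the treated subjects with no usable post-baseline value. None of the m can be a responder, so r is the same under both rules.

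- Protocol rule: r/N.
- Sampled set: r/(N - m).
- Ratio of the second to the first: N/(N - m). This is never below 1, and it equals 1 only when m = 0. If r = 0, both rates are zero.

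**Overall rate, assumed N = 18 and r = 9** (Clopper-Pearson 95% intervals, the method in Protocol 13.2.1):

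| m | Rate on sampled set | 95% CI | Factor |
|---|---|---|---|
| 0 | 9/18 = 50.0% | 26.0 to 74.0 | 1.00 |
| 1 | 9/17 = 52.9% | 27.8 to 77.0 | 1.06 |
| 2 | 9/16 = 56.3% | 29.9 to 80.2 | 1.13 |
| 3 | 9/15 = 60.0% | 32.3 to 83.7 | 1.20 |
| 4 | 9/14 = 64.3% | 35.1 to 87.2 | 1.29 |

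Under the protocol rule the answer stays 9/18 = 50.0% whatever m is.

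**Other assumed rates at N = 18, m = 1 to 4.** 6/18 = 33.3% becomes 35.3% to 42.9%; 12/18 = 66.7% becomes 70.6% to 85.7%.

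**With N = 30.** The factor is 1.03 to 1.15 for m = 1 to 4, so 15/30 = 50% becomes 51.7% to 57.7%.

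**By cohort, one subject without a value.** 1/3 (33%) becomes 1/2 (50%); 3/6 (50%) becomes 3/5 (60%).

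**When a subject can be lost.** The first dose is on Day 57. The first scheduled post-baseline ctDNA sample is at Visit 6, Day 78, which is 78 - 57 = 21 days later. The first serum marker is at Visit 10, Day 148, which is 148 - 57 = 91 days later and matters for subjects whose ctDNA was undetectable at baseline. The Visit 15/End of Treatment schedule includes neither.

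**The case against.** The strongest reply is that nothing in the documents shows that anyone will be missing. Subjects who stop treatment stay in follow-up (Protocol 6.7.2), ctDNA is drawn at every follow-up visit, and the Visit 10 scan and serum marker fall together, so a relapse found at that scan would normally have a sample. This stands: the size is unknown and may be nil.

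Second, the PDS is the protocol's own set (13.2.2.5), and the protocol never names the FAS for biomarker response. Protocol 13.2.3 also has a no-substitution sentence much like SAP 12.2, and it coexists with the non-responder rule. This stands in part. The all-treated denominator is an inference from Protocol 13.3.3.2 and from the evaluable set being only supportive, and SAP 12.2 alone does not repeal the rule. But an SAP that names a sample-dependent set and never restates the rule leaves a programmer no instruction to keep those subjects in. The phrase about any PD parameter in SAP 11.4 could admit a subject with some other sample, but that subject's biomarker result would still be missing and its place in the denominator unstated.

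Third, this is an unpowered Phase 1 trial with intervals far wider than the shift, and listings that would let a reader recount. That limits the consequence. It does not make a one-directional error harmless in the headline rate.

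Four stronger readings are tempting but not supported.

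- A reader might infer that SAP 13.6.1 contradicts 13.8.2, because it says "the full analysis set (FAS) will be the primary analysis set for all efficacy endpoints". That sentence opens with a proviso for exceptions stated elsewhere, and 13.8.2 states one.
- A reader might turn the 5-month median RFS in Protocol 4.6.4 into a rate of lost subjects. That figure is for pancreatic cancer with persistent ctDNA after surgery, and relapse is not the same as having no sample.
- A reader might count the addendum's ctDNA Population as another set that drops early failures. A baseline sample alone qualifies, so it can keep them; the gap there is the unstated denominator.
- A reader might infer that the dose-pooling clause inflates the secondary endpoint. It describes an optional exploratory analysis, names no response rate, and includes the MTD cohort whatever its result.

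**Conclusion.** The point holds as a mismatch between protocol and SAP on the only secondary endpoint, undeclared in SAP 14.0. If the SAP is followed by taking the rate on subjects with samples, that rate can equal or exceed the rate under the protocol rule but cannot fall below it. The factor is N/(N - m): 1.06 to 1.29 for m = 1 to 4 at N = 18, or 50% read as 53% to 64% when 9 of 18 treated respond. The direction rests only on the protocol rule. The size rests on assumed values of r and m, and it is zero if every treated subject has a usable post-baseline value. It would be wrong to say that the rate is inflated; it can be, and only upward. For the addendum's rate, the conclusion is narrower: its denominator and missing-data rule are not stated. The dose-pooling clause is a minor separate point about an optional analysis.

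**What to change.** In SAP 13.8.2, SAP 11.4 and the addendum (section 2.2 and Table 7), state that the proportions with reduction and with clearance are computed on the FAS, by cohort and overall. A subject with no usable post-baseline value before new anti-cancer therapy counts as a non-responder, per Protocol 13.3.3.2. Report m next to each rate. Keep the PDS for by-visit levels and, if wanted, for a rate labelled as supportive. If the sponsor prefers another denominator, list it in SAP 14.0 as a departure with the reason.

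For the exploratory pooled analysis in Protocol 13.2.2.1 and SAP 11.1, define the group by dose, such as all cohorts or all at or above a named level, rather than by whether clearance or reduction was seen.

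The cost is SAP and shell wording and a changed denominator. No new data are needed. The reported rate may be lower.

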**Table 18: Planned Analyses of PD and Immunologic Response Variables**

Assessment	Summary Variables
High Resolution HLA	HLA type will be listed by subject in the demographics and baseline characteristics section
Serum cytokines (IL-2, IFN $\gamma$ , IL-6, IL-10, and TNF $\alpha$ )	Observed results/change from baseline

**13.8.3 Patient Reported Outcomes (PRO)**

Patient Reported Outcomes will be assessed by European Organization for Research and Treatment of Cancer quality of life questionnaire (EORTC), QLQ-C30 and QLQ-PAN26, QLQCR29, QLQ-OV28, QLQ-BIL21 or QLQ-LC13.

A by-subject listing will also be provided.

### 13.8.3.1 EORTC QLQ-C30

The European Organization for Research and Treatment of Cancer quality of life questionnaire (EORTC QLQ-C30) is a tool for assessing the quality of life (QoL) of cancer subjects participating in clinical trials. The EORTC QLQ-C30 incorporates 9 multi-item scales are provided in Table . These scales are scored using the algorithm specified in the section 12.4.1.

### 13.8.3.2 Tumor type-specific PROs

Tumor type-specific PROs are intended to supplement the EORTC QLQ-C30 with questions appropriate for the symptoms experienced by subjects with each tumor type. PRO responses will be listed by subject and visit. Tumor type-specific PROs will include:

- QLQ-PAN26: pancreatic cancer
- QLQ-BIL-21: biliary cancer
- QLQ-CR-29: colorectal cancer
- QLQ-LC-13: lung cancer
- QLQ-OV-28: ovarian cancer

For QLQ-PAN26 symptoms/functional scales are provided in Table and the corresponding scale scores will be calculated (see section 12.4.2).

As per Table and section 12.4.3 QLQ-BIL-21 scales, and the scores will be computed

The QLQ-CR-29 scales are presented in per Table . These scale scores will be derived as specified in section 12.4.4.

The scales for QLQ-LC-13 and QLQ-OV-28 are provided in Table and Table respectively. The corresponding scale scores are computed referring to the sections 12.4.5 and 12.4.6.

## 14.0 CHANGES TO PLANNED ANALYSIS FROM STUDY PROTOCOL

The protocol has indicated that statistical testing and confidence intervals would be computed for the efficacy analyses; however, since the sample sizes are small and efficacy data from this trial are exploratory and not powered to elicit statistically significant treatment effects, no formal statistical testing will be computed except for RFS and OS endpoints. ctDNA and Immunogenicity analyses are beyond the scope of this document and are specified in a separate addendum which is attached here as an appendix.

Additional exposure outcomes namely Dose Intensity (DI) and Relative Dose Intensity (RDI) not mentioned in the protocol will be summarized for better clarity on the treatment exposure.

The protocol has requested that summary statistics be presented for patient reported outcomes, however, due to the early termination of the long term follow up of the study, only by-subject listing will also be provided for these endpoints.

The protocol has requested the use of the Disease Response Evaluable Set population, however, as no outputs in the SAP/shells are based on this set, it was dropped from the SAP.

**Final Analysis  
Statistical Analysis Plan (SAP)**

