### 13.2. General Statistical Considerations and Definitions

#### 13.2.1. General Statistical Methods

As a general approach, continuous variables will be summarized using mean, standard deviation, median, minimum value, and maximum value. Categorical variables will be summarized using frequency counts and percentages. Time to event data will be summarized using the Kaplan-Meier method. Where appropriate, CIs around point estimates will be presented, and estimates of the median and other quantiles, as well as individual time points (for time to event data) will be produced.

All statistical hypothesis testing within (for change from baseline) and between dose cohorts will be conducted at the 1-sided 0.05 level of significance. Nominal p-values may be computed for secondary or exploratory efficacy analyses as a descriptive measure of strength of results rather than for formal tests of hypotheses. Emphasis will be on RP2D, highest dose, and combined RP2D and all higher doses for change from baseline and comparison to lowest dose. No formal tests of hypotheses are planned for safety analyses.

The following methods will be used in this trial for descriptive summaries and hypothesis testing unless otherwise indicated:

- **Mean change from baseline.** Compared to zero change and compared between dose levels using t-tests from repeated measures as the analysis model and/or via non-parametric tests based on ranks, as appropriate.
- **Median time to event for a single group (non-comparative).** The Kaplan-Meier method will be used to estimate median time to event; 2-sided CIs will use the method of Brookmeyer and Crowley; p-values will not be computed.
- **Hazard ratio of a time to event endpoint comparing two groups.** A stratified Cox proportional hazards model using Efron's method for ties will be used to estimate the HR and 2-sided CI; p-values will be computed using the log rank test.

- **Time to event analysis at a fixed time point.** The Kaplan-Meier method will be used to estimate the survival (or event-free) probability; 2-sided CIs for a single survival probability or for a difference of two survival probabilities will use the complementary log-log method; p-values will be computed using the complementary log-log test statistic.

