- **Binary endpoint for a single group (non-comparative).** The binomial parameter (probability of success/failure) will be estimated by the sample proportion. 2-sided CIs will use the method of Clopper and Pearson; p-values will not be computed.
- **Comparison of binary endpoint between two groups.** Difference of sample proportions will be used to estimate the difference in binomial parameters. 2-sided CIs will use Newcombe's score method without continuity correction; p-values will be computed using stratified Cochran-Mantel-Haenszel test.

All descriptive statistical analyses will be performed using SAS statistical software (Version 9.3 or later), unless otherwise noted. Medical History and AEs will be coding using MedDRA.

No adjustment for multiple testing will be made.

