## Final Analysis Statistical Analysis Plan (SAP)

Meier method. Where appropriate, estimates of the median and other quantiles, as well as individual time points (for time to event data) will be produced. The purpose of the efficacy summaries is to document the efficacy findings of this study to inform the design of subsequent studies. All summaries will be presented by cohort/dose levels and overall.

Emphasis will be on RP2D, highest dose, and combined RP2D and all higher doses for change from baseline and comparison to lowest dose.

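### The SAP omits the protocol's confidence intervals for single-group efficacy estimates without clearly saying so, and its sections disagree on what inference remains

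*SAP*

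**What the plan says.** **Protocol.** Section 13.2.1 sets a general rule: "Where appropriate, CIs around point estimates will be presented". It then names methods. For a single-group median, "2-sided CIs will use the method of Brookmeyer and Crowley; p-values will not be computed". For a single-group proportion, "2-sided CIs will use the method of Clopper and Pearson; p-values will not be computed". Event-free probabilities at a fixed time get two-sided complementary log-log intervals. No confidence level is given. The nearest figure is for hypothesis tests, which "will be conducted at the 1-sided 0.05 level of significance".

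**SAP general methods.** Section 13.1 carries the matching sentence without the interval clause: "Where appropriate, estimates of the median and other quantiles, as well as individual time points (for time to event data) will be produced". The same section plans no formal hypothesis tests and allows only nominal p-values.

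**SAP outputs.** Section 13.6.2 gives the RFS median with quartiles, event and censoring counts and Kaplan-Meier plots. Section 13.6.3 is similar for OS. Table 15 gives Kaplan-Meier as the only method for RFS, 1-year RFS and OS. Addendum 2.2 reports ctDNA responders as a number and percentage, and the addendum's Table 7 shell shows the same. None of these lists an interval.

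**SAP 14.0 (changes from protocol).** It begins "The protocol has indicated that statistical testing and confidence intervals would be computed for the efficacy analyses", gives the reason "since the sample sizes are small and efficacy data from this trial are exploratory", and then removes formal testing, except for RFS and OS. It does not go on to say what happens to the intervals.

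**Addendum 1.4.1.** It says intervals will accompany certain parameters identified in later sections. No later section identifies one.

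**The concern.** For single-group medians and proportions the protocol had already separated estimation from testing: it asked for an interval and ruled out a p-value. The SAP's reason for change, small and unpowered samples, bears on testing. An exact interval needs no power, and its width is how a small sample shows what it can and cannot tell.

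SAP 13.1 says the efficacy summaries are meant to inform the design of later studies, and presents them by cohort and overall with emphasis on comparison to the lowest dose. Cohorts hold 3 to 6 subjects. The endpoint definition adds to the problem: Table 8 counts any decrease as a reduction and takes each subject's best biomarker. Rates near 100% are therefore plausible, and without an interval such rates look more certain than they are.

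There is also a documentation problem. Section 14.0 exists to record departures from the protocol. A reader of it cannot tell whether the intervals were dropped on purpose, or what inference is left for RFS and OS.

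**Working it through.** **Sample sizes.** SAP 10.0 plans about 18 subjects, with 3 to 6 in each of three cohorts. 3 × 3 = 9 and 3 × 6 = 18, so the stated figure is the upper bound and not a power result. SAP 8.1 lists five cohorts, which give 5 × 3 = 15 to 5 × 6 = 30. Both 18 and 30 are used below for pooled summaries.

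**Level.** The protocol states none. 95% is assumed; 90% is shown as the two-sided level that corresponds to a one-sided 0.05 test.

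**Proportions (Clopper-Pearson).** For x responders of n, the lower limit is the α/2 quantile of Beta(x, n − x + 1) and the upper limit is the 1 − α/2 quantile of Beta(x + 1, n − x). The lower limit is 0 when x = 0 and the upper limit is 100% when x = n. When x = n the lower limit reduces to (α/2)^(1/n): 0.025^(1/3) = 29.2% and 0.025^(1/6) = 54.1%.

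| Responders | Rate | 95% interval | 90% interval |
|---|---|---|---|
| 0/3 | 0% | 0 to 70.8% | 0 to 63.2% |
| 2/3 | 67% | 9.4 to 99.2% | 13.5 to 98.3% |
| 3/3 | 100% | 29.2 to 100% | 36.8 to 100% |
| 3/6 | 50% | 11.8 to 88.2% | 15.3 to 84.7% |
| 4/6 | 67% | 22.3 to 95.7% | 27.1 to 93.7% |
| 6/6 | 100% | 54.1 to 100% | 60.7 to 100% |
| 9/18 | 50% | 26.0 to 74.0% | 29.1 to 70.9% |
| 15/30 | 50% | 31.3 to 68.7% | 33.9 to 66.1% |

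The counts are illustrative; the documents report no results.

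**Medians.** Take the most favourable case, in which every subject has an event. The interval from the smallest to the largest observed time covers the true median with probability 1 − 2 × 0.5^n: 75% for n = 3, 87.5% for n = 4, 93.75% for n = 5 and 96.9% for n = 6. So no finite distribution-free 95% interval exists for n = 3 to 5. Brookmeyer-Crowley with Greenwood variance agrees. At n = 3 to 5 it rejects no event time before the last, on either the linear or the log-log scale. At n = 6 the log-log version still rejects none, while the linear version rejects the first and the fifth. At n = 18 the interval is bounded, running from about the 5th (log-log) or 6th (linear) ordered event to the 13th. Censoring would generally widen these limits.

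**Consistency of the SAP text.**

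| Place | Tests | Intervals |
|---|---|---|
| 13.1 | none planned | clause absent |
| 13.6.2, 13.6.3 | none described | none described |
| 14.0 | none, except RFS and OS | named as a protocol plan, then not addressed |
| Addendum 1.4.1 | limited | promised for some parameters, none named |

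The RFS and OS exemption in 14.0 conflicts with 13.1 and has no matching method in 13.6.2 or 13.6.3.

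**The case against.** The strongest reply is that this is a descriptive, unpowered phase 1 trial, that the protocol's general rule applies only where appropriate, and that a reader will see plenty besides a point estimate. Much of that stands:

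- RFS comes with quartiles, event and censoring counts and Kaplan-Meier plots under two censoring rules. SAP 13.6 adds time-point estimates, waterfall plots and swimmer plots. Efficacy data are listed by patient, and summaries are overall as well as by cohort. A reader might infer that the RFS and OS medians are left as bare point estimates; that is not so. These displays do show spread and individual outcomes rather than uncertainty in the median, and they supply no uncertainty for the responder proportion.
- A reader might take 14.0 as stating that intervals are dropped. It does not. The omission is visible only by comparing 13.1, 13.6 and the addendum with the protocol.
- Cohort-level limits for medians would mostly not be estimable at n = 3 to 5, so restoring them adds little by cohort beyond showing how little a cohort median can say.
- The main table templates are in a separate document (SAP 6.0) and could contain intervals. The SAP text does not call for them.

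The reply does not rescue the stated reason. The protocol's qualifier leaves room for judgement, but small n is not a ground for calling an exact binomial interval inappropriate.

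**Conclusion.** The point holds as an omission that the SAP does not clearly declare, together with an internal inconsistency about RFS and OS. Followed as written, the SAP reports the trial's only secondary endpoint as a count and percentage. At the assumed 95% level the missing interval would span about 71 percentage points for 3/3 (100 − 29.2), 76 for 3/6 (88.2 − 11.8), and 48 for 9/18 pooled (74.0 − 26.0). Using 90% narrows these without changing the message.

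Two further inferences are not supported:

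- **RP2D.** A reader might infer that the missing intervals could mislead the RP2D choice. The RP2D rests on the MTD, safety and pharmacodynamic data and is communicated after the last Safety Monitoring Committee cohort review. This is a final-analysis SAP, revised when long-term follow-up ended early. The addendum's ctDNA analyses do run after each cohort, but an effect on dose selection is speculative.
- **DLT rate.** A reader might infer that an interval for the DLT rate was dropped too. Section 14.0 concerns efficacy, and the protocol's safety analysis section names no such interval.

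The conclusion rests on an assumed confidence level, illustrative counts, and no censoring in the median calculation.

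**What to change.** 1. Restore two-sided Clopper-Pearson intervals for biomarker reduction and for clearance, by cohort and overall.
2. Restore Brookmeyer-Crowley intervals for median RFS and OS, and complementary log-log intervals for 1-year RFS and any other fixed time point, by cohort and overall. Print NE where a limit cannot be estimated, which should be expected for most cohort medians at n = 3 to 5.
3. State the confidence level, since the protocol gives none, and the transformation used for Brookmeyer-Crowley.
4. Reconcile SAP 13.1, 14.0 and addendum 1.4.1: say whether any test remains for RFS and OS, and either name the parameters that get intervals or delete the promise. If any interval is still to be omitted, 14.0 should say so and give a reason that applies to intervals.

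No tests need to be attached. An interval for the DLT rate would be an optional addition, not a restoration. The cost is a few SAS options and table columns. The only downside is that many limits will be wide or not estimable, which is accurate information for anyone using these results to design a later study.

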## 13.0 STATISTICAL METHODS

### 13.1 General Statistical Conventions

All statistical procedures will be completed using SAS version 9.4 or higher.

No formal tests of hypotheses are planned for analyses described in this document. Nominal p-values may be computed for secondary or exploratory efficacy analyses as a descriptive measure of strength of results rather than for formal tests of hypotheses.

**Unless otherwise stated, all summary tables and summary figures will be presented by cohort/dose level and scheduled visits (if applicable).**

All specified visit assessments described in protocol section 6.1.4 will be included in the analyses. If more than one visit assessments (not labeled as unscheduled) are available, only consider the chronologically most recent assessment for the analyses.

All subject data, including unscheduled visit results and derived data, will be presented in listings sorted by cohort/dose level, scheduled visit, and subject number in chronological order (if applicable).

Efficacy data will be listed by patient. Continuous variables will be summarized using mean, standard deviation, median, minimum value, maximum value; categorical variables will be summarized using frequency counts and percentages; and time to event data will be summarized using the Kaplan-

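### SAP 14.0 exempts RFS and OS from its ban on formal testing, but SAP 13.1 plans no formal tests and SAP 13.6 gives only Kaplan-Meier estimation, so it is unclear whether the protocol's test is kept

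*SAP*

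**What the plan says.** SAP 14.0 lists departures from the protocol. It notes that the protocol foresaw tests and confidence intervals for efficacy. It then gives three reasons for dropping testing (small samples, exploratory data, no power) and concludes that "no formal statistical testing will be computed except for RFS and OS endpoints".

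SAP 13.1 says: "No formal tests of hypotheses are planned for analyses described in this document". It adds: "Nominal p-values may be computed for secondary or exploratory efficacy analyses as a descriptive measure of strength of results". SAP 13.6.1 to 13.6.3 and Table 15 label RFS, 1-year RFS and OS exploratory and give Kaplan-Meier as the only method. Table 16 sets out two RFS censoring rules, headed primary and secondary, and SAP 13.6.2 asks for tables and figures under both.

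Protocol 13.2.1 says: "All statistical hypothesis testing within (for change from baseline) and between dose cohorts will be conducted at the 1-sided 0.05 level of significance". For a two-group time-to-event comparison it names a stratified Cox hazard ratio, and "p-values will be computed using the log rank test". For a fixed time point, "p-values will be computed using the complementary log-log test statistic". It makes no multiplicity adjustment and names no Cox strata. The protocol and SAP 13.1 carry the same sentence on contrasts: "Emphasis will be on RP2D, highest dose, and combined RP2D and all higher doses for change from baseline and comparison to lowest dose". Protocol 8.3 and SAP 8.2 confirm that the trial is open-label and not randomised.

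**The concern.** Sections 14.0 and 13.1 of the SAP cannot both be followed. Read literally, 14.0 makes two exploratory endpoints the only formally tested ones. Yet all three reasons that it gives for dropping tests apply equally to RFS and OS. Protocol 13.2.1 and SAP 13.1 also both treat p-values for exploratory efficacy as descriptive.

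RFS and OS are the efficacy results most likely to be quoted. A p-value presented as a formal test would suggest an error rate that nothing in the plan controls. It would also compare non-randomised cohorts opened in sequence, which differ in enrolment time and length of follow-up. The choices still open would be settled late: the SAP revision history dates version 3.0, which changed the RFS censoring rules, to August 2024, whereas the protocol synopsis gives 2Q2023 for the last enrolment.

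**Working it through.** No figure in the plan needs reproducing. The sample size of about 18 is expressly not power-based; it is the top of the planned range, 3 cohorts × 6 = 18.

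**Step 1: what is fixed and where, if the exception keeps the protocol's rule.**

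| Element | SAP 13.6, Tables 15 and 16 | Elsewhere |
|---|---|---|
| Test | none | log-rank; complementary log-log at a fixed time (protocol 13.2.1) |
| Level | none | 1-sided 0.05 (protocol 13.2.1) |
| Reference group | none | lowest dose (protocol 13.2.1, SAP 13.1) |
| Contrast carrying the test | none | three emphasised, none singled out |
| Cox strata | none | model called stratified, strata not named |
| RFS censoring rule | two, headed primary and secondary, both with full outputs | not tied to a test |
| Formal or nominal | not stated | SAP 14.0 implies formal; SAP 13.1 says nominal |

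The first three rows can be filled from outside SAP 13.6. The last four are not settled in either document.

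**Step 2: number of tests.** The contrasts with the lowest dose are RP2D, highest dose, and RP2D pooled with all higher doses: 3. The analyses are RFS under two censoring rules plus OS: 2 + 1 = 3. Counting log-rank comparisons only, 3 × 3 = 9. If the RP2D is the highest dose, the three contrasts become the same comparison, leaving 1 × 3 = 3.

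**Step 3: chance of at least one false positive.** For m independent tests at 0.05 it is 1 − 0.95^m:

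- m = 9: 1 − 0.95^9 = 0.370
- m = 3: 1 − 0.95^3 = 0.143

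The tests share the lowest-dose cohort, one contrast contains the other two groups, two analyses use the same RFS data, and RFS includes death. This positive correlation makes 37% and 14% ceilings rather than estimates.

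**Step 4: what one such test could detect.** Assume two full cohorts of 6 and equal allocation. Approximate log-rank power is Φ(√(d/4) × |ln HR| − 1.645), where d is the total number of events.

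- d = 12 (every subject has an event), HR 0.5: √3 × 0.693 − 1.645 = −0.444, power 33%
- d = 12, HR 0.3: √3 × 1.204 − 1.645 = 0.440, power 67%
- d = 6: power 21% at HR 0.5 and 43% at HR 0.3

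By the same formula, 80% power at HR 0.5 needs (1.645 + 0.842)² / (0.25 × 0.693²), about 52 events. The approximation is rough at these sizes, but it supports SAP 14.0's own statement that efficacy is not powered.

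**Step 5: intervals.** Protocol 13.2.1 plans 2-sided intervals: Brookmeyer-Crowley for medians and complementary log-log for fixed-time probabilities. SAP 13.1 repeats the protocol's sentence on medians and quantiles without its reference to intervals, and SAP 13.6.2 and 13.6.3 plan none. Whether the exception in 14.0 was meant to keep intervals for RFS and OS cannot be determined from its wording.

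**The case against.** The best defence is that SAP 14.0 lists departures from the protocol, so an exception there most naturally leaves the protocol's rule in force. That rule names the test, level, sidedness and reference group. This stands, and it rules out a stronger reading. A reader might infer that no comparator, test or alpha exists anywhere, so that any RFS or OS test would be invented after seeing open-label data. The documents do not support this. Nor is the grouping free: the RP2D is set from the MTD, safety and pharmacodynamic data, not from RFS or OS.

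It can also be said that both documents call these endpoints exploratory, treat such p-values as descriptive and openly make no multiplicity adjustment, so no error control is claimed. That is true of protocol 13.2.1 and SAP 13.1, and it limits the harm. It is also why the clause in 14.0 is out of place: it alone calls the RFS and OS testing formal.

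A further objection is that 37% overstates the risk. As an estimate it would, so it is given here only as a ceiling. The finding does not depend on it.

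**Conclusion.** The point holds as an internal conflict with a limited gap behind it. SAP 14.0 and 13.1 disagree on whether RFS and OS are formally tested. The SAP does not say whether the protocol's comparison is retained, or which contrast, strata and censoring rule would carry it. If it is retained, up to 9 unadjusted log-rank tests are possible, with a false-positive ceiling of 37%. The ceiling is 14% for 3 tests if the RP2D is the highest dose. Both rest on independence at 1-sided 0.05, and the true values are lower.

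No primary endpoint is affected. What is at risk is the labelling of two unpowered exploratory results, and the loss of the intervals that would show how imprecise they are. The correction is cheap enough to be worth making.

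**What to change.** 1. In SAP 14.0, delete the clause that exempts RFS and OS.
2. In SAP 13.6.2 and 13.6.3, state that RFS and OS are reported as Kaplan-Meier estimates with 2-sided 95% confidence intervals: Brookmeyer-Crowley for medians and complementary log-log for 1-year RFS, the methods already in protocol 13.2.1.
3. Label any between-cohort p-value for RFS or OS nominal and descriptive, in line with SAP 13.1.

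The cost is a few sentences of SAP wording and interval columns in the RFS and OS outputs. No additional data are needed.
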